**Overview**

Protocol I8F-MC-GPGH titled “A Randomized, Phase 3, Open-Label Trial Comparing the Effect of LY3298176 versus Titrated Insulin Degludec on Glycemic Control in Patients with Type 2 Diabetes (SURPASS-3)” has been amended. The new protocol is indicated by amendment (c) and will be used to conduct the study in place of any preceding version of the protocol.

The overall changes and rationale for the changes made to this protocol are described in the following table.

### 3. Revision History

Statistical analysis plan (SAP) Version 1 was approved prior to the first patient receiving study drug.

The second version was approved prior to the final database lock. The following represent major changes made for the second version:

1. Update definition of analysis set: Per agreement with the US FDA, patients that discontinue study drug due to inadvertent enrollment are excluded from efficacy analysis.
2. Update baseline definition for selected measures based on scientific consideration and to minimize missing values at baseline.
3. Update primary endpoint: Missing data imputation. Corrected the definition of “retrieved dropout.” Use of local lab data for glycemic control measures when central lab data are not available.
4. Update the language to handle lack of convergence in longitudinal logistic regression analysis due to low number of events for hemoglobin A1c (HbA1c) and weight loss target analyses.
5. Update the language in section on adverse events of special interest and renamed section to “Special Safety Topics” to be consistent with the program SAP (see Section 6.13.2).
6. Add section to assess SARS-CoV-2 (COVID-19) impact (see Section 6.20).
7. Add an explanation of the unblinding plan that was created for Study GPGH after the initial approval of this analysis plan.

## 4. Study Objectives

### 4.1. Primary Objective

The primary objective of the study is to demonstrate that once-weekly (QW) LY3298176 (tirzepatide) 10 mg and/or 15 mg are noninferior to insulin degludec for change from baseline in hemoglobin (HbA1c) at 52 weeks.

### 4.2. Key Secondary Objectives Subject to Strong Type 1 Error Rate Control

Together with the primary objective, the following secondary objectives are subjected to strong control of the type 1 error rate (see Section 6.12.3).

- To demonstrate that QW tirzepatide 5 mg is noninferior to insulin degludec for change from baseline in HbA1c at 52 weeks.
- To demonstrate that QW tirzepatide 5 mg, 10 mg, and/or 15 mg are superior to insulin degludec for change from baseline in weight at 52 weeks.
- To demonstrate that QW tirzepatide 5 mg, 10 mg, and/or 15 mg are superior to insulin degludec for change from baseline in HbA1c at 52 weeks.
- To demonstrate that QW tirzepatide 5 mg, 10 mg, and/or 15 mg are superior to insulin degludec for the proportion of patients with HbA1c target values of <7.0% (53 mmol/mol) at 52 weeks.

### 4.3. Other Secondary and Exploratory Objectives Not Subject to Type 1 Error Rate Control

The following secondary and exploratory objectives are not subjected to strong control of the type 1 error rate.

Secondary Objectives:

- to demonstrate that QW tirzepatide 5 mg, 10 mg, and/or 15 mg are superior to insulin degludec at 52 weeks for:
  - mean change in fasting serum glucose (central lab) from baseline
  - proportion of patients achieving an HbA1c target values of  $\leq 6.5\%$  (48 mmol/mol) and  $< 5.7\%$  (39 mmol/mol)
  - mean change in 7-point self-monitored blood glucose (SMBG) profiles from baseline
  - proportion of patients who achieved weight loss  $\geq 5\%$ ,  $\geq 10\%$ , and  $\geq 15\%$  from baseline
- to compare tirzepatide 5 mg, 10 mg, and 15mg to insulin degludec at 52 weeks for:

- patient-reported outcomes:
  - Diabetes Treatment Satisfaction Questionnaire status/Diabetes Treatment Satisfaction Questionnaire change
  - Impact of Weight on Self-Perception (IW-SP)
  - Ability to Perform Physical Activities of Daily Living (APPADL)

Exploratory objectives:

- to compare tirzepatide 5 mg, 10 mg, and 15 mg with insulin degludec for the following:
  - change in lipids (total cholesterol, high-density lipoprotein [HDL], very low density lipoprotein [VLDL], and triglycerides [TG])
  - change from baseline in mean body mass index (BMI)
  - mean change in waist circumference
  - biomarkers
  - European Quality of Life dimension (5-level EuroQol-5D [EQ-5D]) scores

#### 4.4. Safety Objectives

To compare the safety of tirzepatide 5 mg, 10 mg, and 15 mg to insulin degludec for:

[figure not shown]
- treatment-emergent adverse events (TEAEs)
- early discontinuation of study drug due to adverse events (AEs)
- adjudicated pancreatic AEs
- serum calcitonin
- incidence of allergic and hypersensitivity reactions
- incidence of treatment-emergent anti-drug antibodies to tirzepatide
- mean change in systolic and diastolic blood pressure and heart rate from baseline
- occurrence of hypoglycemic episodes
- incidence of initiation of rescue therapy for severe, persistent hyperglycemia

## 5. Study Design

### 5.1. Summary of Study Design

Study GPGH is a Phase 3, multicenter, randomized, open-label, parallel-group study that will investigate the effects of treatment with tirzepatide 5 mg, 10 mg, and 15 mg QW compared with titrated insulin degludec in patients with type 2 diabetes mellitus (T2DM) who have inadequate glycemic control on stable doses of metformin, with or without a sodium/glucose cotransporter-2 inhibitor (SGLT-2i). The primary endpoint will be the mean change in HbA1c from baseline to 52 weeks.

Figure GPGH.5.1 illustrates the study design.

Abbreviations: FBG = fasting blood glucose; QD = once daily; QW = once weekly; SGLT-2i = sodium-glucose cotransporter-2 inhibitor; TTT = treat to target.

- Stable doses of metformin ( $\geq 1500$  mg/day)  $\pm$  SGLT-2i for  $\geq 3$  months prior to Visit 1 and during the screening/lead-in period.
- The starting dose of insulin degludec will be 10 IU/day ideally at bedtime, titrated to a FBG  $< 90$  mg/dL, following a TTT algorithm.

**Figure GPGH.5.1. Illustration of study design for Clinical Protocol I8F-MC-GPGH.**

#### Study Period I (Screening and Lead-in)

##### Screening (Visit 1)

The purpose of screening procedures at Visit 1 is to establish initial eligibility and to obtain blood samples for laboratory assessments needed to confirm eligibility at Visit 2. Patients who meet all applicable inclusion criteria and none of the applicable exclusion criteria at Visit 1 will continue on their prestudy therapy between Visits 1 and 2.

*Lead-in (Visit 2 to Visit 3)*

At Visit 2, the screening laboratory results will be reviewed and patient eligibility will be established with the exception of retinopathy status. A dilated fundoscopic exam will be performed between Visit 2 and Visit 3 as results are required to confirm eligibility.

**Study Period II (52-Week Treatment Period)***Randomization (Visit 3)*

At Visit 3, eligible patients will perform all required baseline study procedures (including the collection of all baseline laboratory measures) prior to randomization and prior to taking the first dose of study drug.

*Postrandomization period (end of Visit 3 to Visit 24)*

The starting dose of tirzepatide will be 2.5 mg QW for 4 weeks, followed by an increase to 5 mg QW, for the duration of the study in the 5 mg group. For the 10 mg group, the starting dose of tirzepatide will be 2.5 mg QW for 4 weeks, then the dose will be increased by 2.5 mg every 4 weeks (2.5 to 5 to 7.5 to 10 mg) until the 10 mg dose is reached and maintained for the duration of the study. For the 15 mg group, the starting dose of tirzepatide will be 2.5 mg QW for 4 weeks, then the dose will be increased by 2.5 mg every 4 weeks (2.5 to 5 to 7.5 to 10 to 12.5 to 15 mg) until the 15 mg dose is reached and maintained for the duration of the study.

The initial dose of insulin degludec will be 10 IU/day ideally at bedtime, titrated to a fasting blood glucose (FBG) <90 mg/dL, following a treat-to-target (TTT) algorithm.

**Study Period III (Safety Follow-up Period)***Safety follow-up (Visit 801) visits*

All patients who complete the treatment period are required to complete Visit 801, a safety follow-up visit, approximately 4 weeks after their last visit. Patients discontinuing the study early and performing an early termination (ET) visit will also be asked to perform the safety follow-up visit, so that the safety follow-up visit will be their final visit. During the safety follow-up period, patients will not receive study drug. Patients will be treated with another glucose-lowering intervention decided upon by the investigator. Initiation of new antihyperglycemic therapy for the safety follow-up period will not be classified as “rescue therapy.”

**5.2. Determination of Sample Size**

Approximately 1420 patients (355 per group) may be randomly assigned in a 1:1:1:1 ratio to tirzepatide 5, 10, 15 mg QW, or insulin degludec. Patient randomization will be stratified based on country, baseline concomitant oral medication (metformin alone or metformin plus SGLT-2i), and baseline HbA1c ( $\leq 8.5\%$  or  $> 8.5\%$  [69 mmol/mol]).

Although the primary objective of the trial is to demonstrate that once-weekly 10 and/or 15 mg tirzepatide doses are noninferior to titrated insulin degludec relative to mean change in HbA1c

from baseline (using a 0.3% noninferiority boundary), the study is powered to assess superiority of tirzepatide 10 and/or tirzepatide 15 mg QW to insulin degludec, relative to the primary endpoint: mean change in HbA1c from baseline to 52 weeks.

The power is assessed based on the following assumptions:

- each of the 10 and 15 mg tirzepatide QW treatment groups will be tested in parallel against insulin degludec at a 2-sided 0.025 significance level.
- use of a 2-sample t test utilizing HbA1c data collected before initiation of any rescue medication or premature treatment discontinuation with no more than 28% of patients initiating any rescue medication or prematurely discontinuing treatment in each treatment group
- a 0.35% greater mean reduction in HbA1c from baseline for 10 and 15 mg of tirzepatide compared with insulin degludec
- a superiority margin of 0.05%
- a common standard deviation of 1.1%

On the basis of these assumptions, randomly assigning approximately 1420 patients to the 4 treatments using a 1:1:1:1 ratio is required to ensure at least 90% power to demonstrate superiority of tirzepatide 10 mg and/or 15 mg QW doses to insulin degludec, relative to the primary endpoint for the “efficacy” estimand. Furthermore, this sample size will ensure 90% power to demonstrate superiority for the “treatment-regimen” estimand conducted using an analysis of covariance (ANCOVA) utilizing all available HbA1c data at 52 weeks, with missing data imputed with a conservative multiple imputation method (as described in Section 6.12.1.3) if the SD were to increase up to 1.3% due to the inclusion of data on rescue medications, inclusion of data after premature treatment discontinuation, and imputation of the missing data.

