## 10. Statistical Considerations

### 10.1. Sample Size Determination

Patients will be randomized in a 1:1:1:1 ratio to LY3298176 5 mg, 10 mg, 15 mg, or insulin degludec. Although the primary objective of the trial is to demonstrate that once-weekly 10 mg and/or 15 mg doses are noninferior to titrated insulin degludec relative to mean change in HbA1c from baseline (using a 0.3% noninferiority boundary), the study is powered to assess superiority of LY3298176 10 mg and 15 mg, each tested in parallel against titrated insulin degludec at a 2-sided significance level of 0.025, relative to the primary endpoint (mean change in HbA1c from baseline to 52 weeks), under the following assumptions: use of a 2-sample t-test utilizing HbA1c data collected before initiation of any rescue medication or premature treatment discontinuation with no more than 28% of subjects initiating any rescue medication or prematurely discontinuing treatment in each treatment group; 0.35% greater mean reduction in HbA1c from baseline for 10 and 15 mg LY3298176 compared with insulin degludec; 1:1:1:1 randomization, a common standard deviation (SD) of 1.1%, and a superiority boundary of 0.05%. On the basis of these assumptions, a sample size of 1420 subjects is required to ensure at least 90% power to demonstrate that LY3298176 10 mg and/or 15 mg are superior to insulin degludec relative to the primary endpoint. Furthermore, this sample size will ensure 90% power for the superiority evaluation conducted using an analysis of covariance (ANCOVA) utilizing all available HbA1c data at 52 weeks with missing data imputed with a conservative multiple imputation method (as described in the Efficacy Analysis section below), provided a 0.35% greater mean reduction in HbA1c from baseline for 10 and 15 mg LY3298176 compared with insulin degludec and SD increases to no more than 1.3% due to the inclusion of data on rescue medications and after premature treatment discontinuation, and imputation of missing data.

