## **6.12.2. Secondary Efficacy Analyses Subject to Type 1 Error Rate Control**

### **6.12.2.1. Mean Change in HbA1c from Baseline at the 52 Week Visit**

Noninferiority of 5 mg LY3198176 to insulin degludec will be conducted in a manner similar to Section 6.12.1. Assessment of Superiority of tirzepatide doses compared to insulin degludec will be conducted using the same statistical models as those used for evaluating the primary objective in Section 6.12.1. Decisions will be guided by the 2-sided p-values for mean comparisons between tirzepatide doses and insulin degludec (see details in Section 6.12.3).

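### Does the 0.05% superiority boundary, used for the sample size but absent from the superiority test, undermine the stated 90% power?

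*SAP*

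**What the plan says.** Protocol 10.1 and SAP 5.2 give the same planning basis. Each of the 10 mg and 15 mg doses "will be tested in parallel against insulin degludec at a 2-sided 0.025 significance level". The assumed effect is "a 0.35% greater mean reduction in HbA1c from baseline for 10 and 15 mg of tirzepatide compared with insulin degludec". The protocol adds "a common standard deviation (SD) of 1.1%, and a superiority boundary of 0.05"%, and the SAP lists "a superiority margin of 0.05"% as a separate item. At most 28% of patients per arm are expected to start rescue or stop treatment early. From this the protocol concludes that "a sample size of 1420 subjects is required to ensure at least 90% power to demonstrate that LY3298176 10 mg and/or 15 mg are superior". Both documents also claim 90% for the treatment-regimen estimand; in the SAP's words this holds "if the SD were to increase up to 1.3% due to the inclusion of data on rescue medications", post-discontinuation data and imputation.

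The decision rule is in the analysis sections. SAP 6.12.1.4 says superiority is examined once noninferiority is shown. SAP 6.12.2.1 says: "Decisions will be guided by the 2-sided p-values for mean comparisons between tirzepatide doses and insulin degludec", and refers to 6.12.3 for details. The numbered steps in 6.12.3 give significance levels and an order of testing. None of these sections mentions 0.05%.

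**The concern.** A sample size should be worked out for the test that will be run. Here the planning sections subtract 0.05 from the assumed effect, while the analysis sections on their ordinary reading compare the difference with zero. The SAP does write a margin into its decision rule where one governs: the 0.3% noninferiority margin is a confidence-limit rule in 6.12.1.1 and 6.12.1.2. Nothing similar exists for 0.05%, and neither document calls it a planning allowance only.

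Two things could follow. First, superiority on HbA1c is the claim the trial is powered on, and it is under type 1 error control. If an upper confidence limit fell between −0.05% and 0, a reader who applied the planning boundary would reach the opposite verdict to one who applied 6.12.2.1. Second, a reader might take the 90% as the power of each dose under the listed assumptions, when with the boundary each dose has only about 80%.

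**Working it through.** **Inputs** (SAP 5.2, protocol 10.1): 355 per arm; 2-sided 0.025 per dose, so the critical value is z = 2.2414; true difference 0.35; boundary 0.05. For the efficacy estimand, SD 1.1 and 355 × 0.72 = 255.6 evaluable per arm. For the treatment-regimen estimand, SD 1.3 and all 355 per arm.

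**Per-dose power:** Φ(d / SE − 2.2414), with SE = SD × √(2/n). With the boundary d = 0.35 − 0.05 = 0.30; against zero d = 0.35.

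- Efficacy: SE = 1.1 × √(2/255.6) = 0.0973. With the boundary, 0.30/0.0973 − 2.2414 = 0.842, giving 80.0%. Against zero, 0.35/0.0973 − 2.2414 = 1.356, giving 91.2%.
- Treatment regimen: SE = 1.3 × √(2/355) = 0.0976. With the boundary, 0.833, giving 79.8%. Against zero, 1.345, giving 91.1%.

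The noncentral t gives 79.8%, 91.1%, 79.6% and 91.0% in the same order.

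**Joint power:** the two comparisons share one control arm of equal size, so their test statistics have correlation 0.5. A bivariate normal with equal effects gives:

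| Estimand | Null value | Each dose | At least one | Both |
|---|---|---|---|---|
| Efficacy | boundary | 80.0% | 91.3% | 68.7% |
| Efficacy | zero | 91.2% | 97.3% | 85.2% |
| Treatment regimen | boundary | 79.8% | 91.1% | 68.4% |
| Treatment regimen | zero | 91.1% | 97.2% | 84.9% |

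The plan's own figure is the at-least-one column with the boundary: 91.3% and 91.1%, which agrees with the stated 90%.

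**Total size for 90% power** (per-arm number × 4; efficacy, then treatment regimen):

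- boundary, at least one dose: 341 × 4 = 1364; 342 × 4 = 1368
- boundary, each dose: 464 × 4 = 1856; 467 × 4 = 1868
- zero, each dose: 342 × 4 = 1368; 343 × 4 = 1372
- zero, at least one dose: 250 × 4 = 1000; 251 × 4 = 1004

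The planned 1420 covers the first and third cases for both estimands, with a little to spare. It covers the fourth with much to spare. Only the second would need more patients, and neither document claims it.

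**How far the two rules differ:** for the efficacy estimand, the test against zero succeeds when the estimated difference is below −2.2414 × 0.0973 = −0.218. With the boundary it would have to be below −0.268. If the true difference is −0.35, the estimate for a given dose falls between these two values with probability 91.2% − 80.0% = 11.2%.

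**The case for a change.** The strongest case for a change is that the wording pulls two ways. Protocol 10.1 speaks of each dose being tested in parallel and then claims 90% for one or both. The treatment-regimen sentences claim 90% without repeating the and/or. Two readings land near 1420: the boundary with at least one dose, and no boundary with each dose. A reader cannot be sure which was meant. For the test as written and the and/or claim, about 1000 patients would be enough, so calling 1420 required is loose. The 11-point zone above is also not negligible if someone did apply the boundary to the results.

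Much of this is right as description. The documents do not say what the 0.05% is for, and a sentence to that effect would have helped. But an assumption in a sample-size section is not a decision rule. The SAP has a decision rule in the section where an analyst would look for it, and a p-value for a mean comparison with no stated null value is a test of no difference. An analyst following 6.12.2.1 and 6.12.3 would run that test, and it keeps its 0.025 level per dose against a null of zero. Nor is the stated power wrong under either reading: at least 90% holds with the boundary for at least one dose, and against zero for each dose as well. The figure of about 1000 patients appears only after removing an assumption that the sponsor chose to make.

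Deleting the boundary from SAP 5.2 would gain little. The section would then report about 97% for at least one dose and leave 1420 unexplained for the and/or claim, in a version approved shortly before final database lock.

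**Conclusion.** No change to the plan is called for. The planning sections carry a 0.05% boundary that the visible superiority rule does not use, and the gap runs in the safe direction: the sample size was set for a harder test than the one to be run. Power for at least one dose is about 91% with the boundary and about 97% without it; per dose it is about 80% and about 91%. The stated floor of 90% is met for the event to which the documents attach it, for both estimands. The number of patients, the type 1 error rate and the result of the planned test stay the same whether or not the wording is tidied.

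This rests on several assumptions. Both doses have the same true effect of 0.35%. The statistics have correlation 0.5 from the shared control arm. Covariates bring no gain in precision. The 28% contribute nothing to the efficacy analysis. The superiority test is taken on its own, without the earlier steps of the hierarchy. Figure GPGH.6.1 was not shown in the text examined, so a boundary stated only there cannot be ruled out. In that case the test would match the planning assumption, and the 91% for at least one dose would apply.

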### 5.3. Method of Assignment to Treatment

Approximately 1420 patients who meet all criteria for enrollment will be randomized to 1 of the study treatment arms at Visit 3. Assignment to treatment arms will be determined by a computer-generated random sequence using an interactive web response system (IWRS).

Patients will be randomized in a 1:1:1:1 ratio to receive 5 mg tirzepatide, 10 mg tirzepatide, 15 mg tirzepatide, or insulin degludec titrated to achieve a FPG <90 mg/dL. The randomization will be stratified by country, baseline HbA1c concentration ( $\leq 8.5\%$ ,  $>8.5\%$  [ $\leq 69$ ,  $>69$  mmol/mol]), and use of concomitant oral antidiabetic medications (OAMs) (metformin alone, metformin plus an SGLT-2i).

## 6. A Priori Statistical Methods

### 6.1. Populations for Analyses

For purposes of analyses, [Table GPGH.6.1](#) defines the following analysis sets:

**Table GPGH.6.1. Description of Analysis Datasets**

Analysis Set	Description
Screened population	All participants who sign informed consent
Randomized population	All patients who are randomly assigned a treatment arm
modified intention-to-treat (mITT) population	All randomly assigned participants who are exposed to at least 1 dose of study drug. In the event of a treatment error, participants will be analyzed according to the treatment they were randomized.
Efficacy analysis set (EAS)	Data obtained during Study Period II from the mITT population, excluding patients discontinuing study drug due to inadvertent enrollment and data after initiating rescue antihyperglycemic medication or stopping study drug (last dose date +7 days).
Full analysis set (FAS)	All available data obtained during Study Period II from mITT, excluding patients discontinuing study drug due to inadvertent enrollment, regardless of adherence to study drug or initiation of rescue antihyperglycemic medication.
Safety analysis set (SS)	Data obtained during Study Periods II or III from the mITT population, regardless of adherence to study drug or initiation of rescue antihyperglycemic medication.

### 6.2. General Considerations

Statistical analysis of this study will be the responsibility of Eli Lilly and Company (Lilly) or its designee. All statistical analyses will be conducted with SAS Version 9.4 or higher unless otherwise stated. Any change to the data analysis methods described in the protocol will require an amendment only if it changes a principal feature of the protocol. Any other changes to the data analysis methods described in the protocol, and the justification for making the change, will be described in the SAP or the clinical study report (CSR). Some analyses and summaries described in this analysis plan may not be conducted if not warranted by data (e.g., few events to justify conducting an analysis). Listings of events will be provided in such situations. Additional analyses of the data may be conducted as deemed appropriate without further changes made to the protocol or SAP, even after the primary or final database locks (DBL).

Patients inadvertently receiving incorrect study treatment are expected to switch to their randomized treatment arm as soon as possible. Patients assigned to tirzepatide may not be able to tolerate the maximum dose of the randomized treatment arm and may continue study participation on a reduced maintenance dose. Continuing on a reduced maintenance dose will neither be considered as discontinuation of randomized treatment nor will be considered as non-compliant to randomized treatment. Additionally, to avoid potential selection biases, unless stated otherwise, statistical summaries and analyses will be conducted based on randomized maintenance dose regardless of the actual treatment received by the patient.

Unless specified otherwise, the last measurement during Visit 1 to Visit 3 (including unscheduled visits) collected prior to or on the first dose day will serve as baseline. For immunogenicity, data collected up to the first dose time will serve as baseline. For lab and electrocardiogram (ECG), baseline needs to be prior to or within 1 hour after the first dose time. For patient-reported outcomes, data collected at Visit 3, regardless of the timing relative to first dose, will serve as baseline.

There will be 2 estimands of interest in evaluating primary and secondary efficacy objectives. The first estimand, the “efficacy” estimand, represents efficacy prior to discontinuation of study drug without confounding effects of rescue therapy for persistent severe hyperglycemia. Analysis relative to the “efficacy” estimand will be conducted using the efficacy analysis set (EAS). The second estimand, the “treatment-regimen” estimand (including all data), represents the efficacy irrespective of adherence to investigational product or introduction of rescue therapy for persistent severe hyperglycemia. Analyses relative to the “treatment-regimen” estimand will be conducted using the full analysis set (FAS).

Unless specified otherwise, safety analyses will be conducted relative to the “treatment-regimen” estimand using the safety analysis set (SS).

End of study participation for a patient will be the earliest of date of death, date of withdrawal from further participation in the study, or date of safety follow-up visit (Visit 801). For patients considered to be lost-to-follow-up, end of study participation will be the date of lost-to-follow-up reported by the investigator. Patient data included in the database after the last date of study participation (date of early termination or date of safety follow-up) will be excluded from statistical analysis. Listings of such data will be provided.

Summary statistics for categorical measures (including categorized continuous measures) will include sample size, frequency, and percentages. Summary statistics for continuous measures will include sample size, mean, standard deviation (SD), median, minimum, and maximum. The summary statistics will be presented by nominal visit.

Statistical treatment comparisons will only be performed between tirzepatide doses and insulin degludec. Since the trial is not adequately powered to detect difference among tirzepatide doses, comparisons among tirzepatide arms will not be performed unless otherwise specified.

Statistical summaries and results of statistical analyses will be displayed in the following treatment order: 5 mg tirzepatide, 10 mg tirzepatide, 15 mg tirzepatide, insulin degludec.

